5.3.6.2. Montreal Cognitive Assessment (MoCA)

The MoCA ([Nasreddine 2005](#)) is a brief cognitive screening tool that is used in clinical research and practice. The scores range from 0 to 30 with scores lower than 26 suggesting cognitive disorder. The MoCA includes measures of expressive and receptive language, memory, and praxis. There are items that screen executive functions and working memory.

5.3.6.3. Geriatric Depression Scale-30 (GDS-30)

The GDS is a 30-item self-administered yes/no question test constructed for brief screening of depression in elderly persons ([Yesavage 1983](#)). Scores greater than 9 are considered suspect for depression.

5.3.6.4. Alzheimer's Disease Cooperative Study-Clinical Global Impression of Change (ADCS-CGIC)

The ADCS-CGIC focuses on clinicians' observations of change in the patient's cognitive, functional, and behavioral performance since the beginning of a trial ([Schneider 1997](#)). It relies on both direct examination of the patient and interview of informants. Unlike a targeted symptom scale, it takes into account a subject's overall function in the cognitive, behavioral, and functional activity domains. Scoring is based on an interview with the caregiver and examination of the patient by an independent evaluator. The MoCA will be used to provide the cognitive assessment. The ADCS-CGIC requires the assessor to consider a number of cognitive, functional, and behavioral areas prior to providing an overall "global" assessment of clinical change. It is performed by interviewing the patient to assess function and mental status and the informant, using a worksheet that comprehensively lists relevant symptoms potentially useful in judging clinically meaningful change, and allows for notes for future reference.

5.3.6.5. Starkstein Apathy Scale short form (SAS-6)

The SAS-6 is a 6-item questionnaire to measure the severity of apathetic symptoms ([Garofalo 2021, Starkstein 1992](#)). In the SAS-6, each question is read by the examiner, and the patient is provided with four possible answers: "not at all," "slightly," "some," or "a lot" which are scored on a 4-point Likert scale (range: 0–3). Scores range from 0 to 18; higher scores indicate more severe apathy.

5.3.6.6. Connors Adult ADHD Rating Scale – self-report short form (CAARS)

The CAARS is an 26-item scale designed to assess, diagnose, and monitor treatment of attention deficit/hyperactivity disorder (ADHD) in adults. The self-report short form contains factor-derived scales for inattention/memory, hyperactivity/restlessness,

impulsivity/emotional lability, and problems with self-concept (developed by Conners, Erhardt, and Sparrow, unpublished).

5.3.6.7. REM Sleep Behavior Disorder Single-Question Screen (RBD1Q)

The RBD1Q is a single “yes-no” question that queries the classic dream-enactment behavior of RBD ([Postuma 2012](#)) and will be administered at Screening to identify subjects with REM sleep behavior disorder.

The RBD1Q consists of a single question, answered “yes” or “no,” as follows: “Have you ever been told, or suspected yourself, that you seem to ‘act out your dreams’ while asleep (for example, punching, flailing your arms in the air, making running movements, etc.)?”

RBD1Q will be evaluated and recorded for all subjects, but to be used to assess eligibility for subjects with PD only.

5.3.6.8. Modified Hoehn and Yahr Scale (MHYS) for subjects with PD only

The MHYS is a clinician-completed rating scale that is used to describe the symptom progression of PD. Originally described in 1967, it parsed the progression of PD into 5 stages. It has since been modified with the addition of stages 1.5 and 2.5 to account for the intermediate course of PD ([Fahn 1987](#)). As such, the MHYS is as follows:

- Stage 0: No signs of disease.
- Stage 1.0: Unilateral disease.
- Stage 1.5: Unilateral plus axial involvement.
- Stage 2: Bilateral disease, without impairment of balance.
- Stage 2.5: Mild bilateral disease, with recovery on pull test.
- Stage 3: Mild to moderate bilateral disease; some postural instability; physically independent.
- Stage 4: Severe disability; still able to walk or stand unassisted.
- Stage 5: Wheelchair bound or bedridden unless aided.

The MHYS will be evaluated during screening (unless completed within the past 3 months) for purposes of phenotyping of subjects with PD. It will not be used as an enrollment criterion.

5.3.6.9. CANTAB Assessments

The CANTAB is a standardized and automated administration of cognitive testing via touch tablet, which will include the following:

- The Reaction Time (RTI) task is a processing and psychomotor speed task. It begins with a simple stage with only one target and can be increased to 5 targets to increase demand. Once a yellow circle flashes on screen, subjects must select that circle as fast as possible.
- The Verbal Recognition Memory (VRM) Phase I and Delayed Verbal Recall recognition measures the ability to encode and subsequently retrieve verbal information. Eighteen (18) words are presented, and subjects are subsequently asked

to recall them; this is repeated 2 times. Forty-five (45) minutes later free recall test and forced-choice recognition test are carried out.

- The Adaptive Tracking Task (ATT) measures visuomotor coordination and vigilance. In this test, a small circle (target) will continuously move across the screen in a semi-randomized fashion, so as to minimize the subject's ability to predict the trajectory of the target. The subject is instructed to use his/her finger upon the touch screen to move a small dot so that it is consistently within the center of the moving target on the screen. During the test, the speed of the circle is adjusted in response to the subject's ability to keep the dot in the circle, ensuring that the test is adapted to the individual subject.
- The Paired Associates Learning (PAL) task is a measure of visuo-spatial episodic memory relying on the functional integrity of the hippocampus. The task becomes gradually more difficult, benchmarking a subject's memory capacity. Subjects have to remember the location of an abstract pattern in a specific location.
- The Stop Signal Task (SST) measures response inhibition (impulse control). The subject must respond to an arrow stimulus, by selecting one of two options, depending on the direction in which the arrow points. If an audio tone is present, the subject must withhold making that response (inhibition).

5.3.6.10. Phonological Verbal Fluency Test (pVFT)

Verbal fluency tests are widely used for assessing executive function and requires the generation of words from initial letters (phonological verbal fluency) or belonging to a specific category (semantic fluency), under a time constraint ([Harrison 2000](#)). The specific versions of verbal fluency used in this study are the 'ALPHABET' and 'CATEGORY' tests from the Brief And Simple Index of Cognition (BASIC) (Metis Cognition, Ltd., Warminster, UK).

For the ALPHABET task, subjects are given 1 minute to say aloud as many words they can think of that begin with the letter F, avoiding repetitions or the same words with different endings. The total score is the number of correct words generated.

For the CATEGORY task, subjects are given 1 minute to say aloud as many animals they can think of, avoiding repetitions. The total score is the number of animals generated.

5.3.6.11. Facial Expression Recognition Task (FERT)

The Facial Expression Recognition Task assesses the recognition of facial emotions. Faces with six different basic emotions (happiness, fear, anger, disgust, sadness, surprise) are briefly displayed on the screen and participants are required to indicate the expression of the face via a button-press. Different intensity levels of each emotion are presented, which increases the ambiguity of the facial expression and the sensitivity of the task. Early change in measures of emotional bias in depressed patients treated with antidepressants has been positively correlated with the improvement in patients' symptoms of depression across a full

6–8 weeks of treatment ([Tranter 2009](#)) suggesting that such early changes detected through the use of the FERT may be predictive of antidepressant response.

5.3.6.12. Color Trails Test (Select Sites Only)

The Color Trails Test consists of numbered circles printed with vivid pink or yellow backgrounds that are perceptible to color-blind individuals. For Part 1, the respondent uses a pencil to rapidly connect circles numbered 1-25 in sequence. For Part 2, the respondent rapidly connects numbered circles in sequence, but alternates between pink and yellow. The length of time to complete each trial is recorded.

5.4. Concomitant Medications

Subjects who require routine medication to manage and treat concurrent conditions (e.g., hyperlipidemia, diabetes, hypertension, Parkinson's Disease, Alzheimer's Disease) must be on stable doses 30 days prior to randomization and remain on those doses for the duration of the study. Any concomitant therapy taken from the time the subject signs the informed consent through the final visit must be recorded on the CRF for all enrolled subjects. The medication name, dosage, date, and indication for use must be recorded. The Medical Monitor or designee should be notified in advance of (or as soon as possible after) any instances in which prohibited therapies are administered.

Prohibited concomitant medications include the following:

- Monoclonal antibodies for treatment of MCI or mild dementia e.g., aducanumab.
- Cannabis and products containing tetrahydro cannabinol (THC) and/or cannabidiol (CBD).
- Hypnotics, such as zolpidem or zopiclone, within 48 hours prior to a study visit involving cognitive testing.
- St. John's Wort, green tea, green tea products, or Ginkgo Biloba during Screening or throughout the study.
- Benzodiazepines from Screening throughout the study with the following exception:
 - Clonazepam is permitted when used for RBD at doses up to 1 mg at bedtime – subjects must be on a stable dose 90 days prior to randomization and remain on that dose throughout both treatment periods.
- Anti-psychotic medication(s) are permitted at stable doses 90 days prior to randomization. The doses must remain unchanged throughout both treatment periods.
- Gabapentin 900 mg per day maximum, gabapentin enacarbil 600 mg per day maximum, pregabalin 300 mg per day maximum are permitted at stable doses 90 days prior to randomization. The doses must remain unchanged throughout both treatment periods.
- Phenylephrine and pseudoephedrine are prohibited from Screening throughout the study.

- Any β -AR agonists or β -AR blockers (including oral medications, eye drops with adrenergic agents such as timolol or atenolol, IV, or inhaled), or any medications that impact adrenergic signaling within the last month prior to Screening and throughout the study, including:
 - β -AR agonists such as Ventolin (albuterol), Proventil (albuterol), Proair HFA (albuterol), Xopenex HFA (levalbuterol), Xopenex (levalbuterol), terbutaline, metaproterenol, Proair Respclick
 - β -AR blockers such as Acebutolol, Atenolol (Tenormin), Bisoprolol (Zebeta), Metoprolol (Lopressor, Toprol XL), Nebivolol (Bystolic), Propranolol (Inderal, InnoPran XL).
- Serotonin-noradrenaline reuptake inhibitors (SNRIs) such as desvenlafaxine (Pristiq, Khedezla), duloxetine (Cymbalta, Irenka), levomilnacipran (Fetzima), milnacipran (Savella), venlafaxine (Effexor XR).
- Tricyclic antidepressants (TCAs) such as Amitriptyline, Amoxapine, Desipramine (Norpramin), Doxepin, Imipramine (Tofranil), Nortriptyline (Pamelor), Protriptyline, Trimipramine.
- Noradrenaline reuptake inhibitors (NRIs) such as atomoxetine, maprotiline, reboxetine, and viloxazine.
- Amphetamines such as dextroamphetamine, methylphenidate, dexmethylphenidate, methamphetamine, mixed amphetamine salts, amphetamine sulfate, lisdexamfetamine.
- Subjects who had prior treatment with any investigational drug \leq 90 days prior to dosing (Day -1), or \leq 5 half-lives of the drug (whichever is longer) will be excluded.
- Subjects should not receive the influenza vaccine within 2 weeks of the Screening visit through to the End-of-Study Visit.
- Opioid use is prohibited within 30 days prior to Screening and throughout the study.

5.5. Escape/Rescue Medications

Since CST-2032 is being co-administered with the nonselective β -AR antagonist nadolol (CST-107), the typical β -AR agonist effects such as HR increases, are unlikely to occur. However, if there are intolerable HR/BP increases subjects may be administered rescue nadolol.

Nadolol has been successfully used in ongoing or previous CuraSen studies to block the peripheral effects of CST-2032 and other β -AR agonists.

5.6. Contraception

Female subjects of childbearing potential (i.e., not postmenopausal or not surgically sterile) and all male participants with sexual partners of childbearing potential must use reliable methods of birth control during their participation in the study.

Unless confirmed to be azoospermic (vasectomized or secondary to medical cause), male subjects must agree to use a male condom from Day -1 throughout the study when having

penile-vaginal intercourse with a woman of childbearing potential who is not currently pregnant. Men with a pregnant or breastfeeding partner must agree to remain abstinent from penile-vaginal intercourse or use a condom during each episode of penile-vaginal penetration until after the End-of-Study Visit.

Female subjects of childbearing potential who have a male partner must agree to contraception from the start of Screening through 30 days after the last administration of study medication.

Acceptable methods of contraception for female subjects of child-bearing potential study include the following:

- Use of highly effective birth control, including hormonal prescription oral contraceptives, contraceptive injections, contraceptive patch, contraceptive implant, contraceptive ring, intrauterine device, intrauterine hormone-releasing system, dual barrier method (e.g., condoms, or diaphragm, or cervical cap when used with spermicide), or
- monogamous relationship with a male partner of confirmed sterility, or
- practice complete abstinence, i.e., refrain from sexual intercourse.

Periodic abstinence (calendar, symptothermal, post-ovulation methods), withdrawal (coitus interruptus), spermicides only, and lactational amenorrhoea method are not acceptable methods of contraception.

The reliability of sexual abstinence needs to be evaluated in relation to the duration of the clinical trial and the preferred and usual lifestyle of the subject.

Females of non-childbearing potential may be enrolled if it is documented that they are postmenopausal (amenorrhea for ≥ 12 months) and follicle-stimulating hormone (FSH) ≥ 25 IU/L, or have undergone surgical sterilization, including hysterectomy, bilateral oophorectomy, bilateral salpingectomy, or Essure procedure. Females with FSH <25 IU/L must agree to contraception from Day -1 through 30 days after the last administration of study medication, if they have a male partner.

6. ASSESSMENT OF SAFETY

Blinded safety data, including adverse events, vitals, ECG, clinical labs, will be monitored and evaluated on an ongoing basis throughout the study.

6.1. Adverse Events

6.1.1. Definitions

Adverse Event

An AE is any untoward medical occurrence associated with the use of a study drug in humans and which does not necessarily have a causal relationship with this treatment. AEs

may be reported by the subject, discovered through Investigator questioning, or detected through physical examination, laboratory test, or other means.

AEs include:

- Any new undesirable medical experience or an unfavorable and unintended change of an existing condition that occurs during or after treatment, whether or not considered related to study medication.
- Abnormal laboratory findings considered by the Investigator to be clinically significant, i.e., those that are unusual for the population being studied or individual subject.
- Complications and termination of pregnancy; uncomplicated pregnancies are not considered AEs but must still be reported.

Additionally, events (including intercurrent illnesses) occurring from the time of randomization will be documented on the AE CRF. Concurrent illnesses, which existed prior to first dose in the clinical trial, will not be considered AEs unless they worsen during the treatment period.

Serious Adverse Event

An SAE is defined as any untoward medical occurrence that at any dose:

- Results in death.
- Is life-threatening (this means that the subject is at risk of death at the time of the event; it does not mean that the event hypothetically might have caused death if it were more severe).
- Requires or prolongs subject hospitalization.
- Results in persistent or significant disability or incapacity.
- Is a congenital anomaly or birth defect.
- Is an important medical event that does not otherwise meet the criteria for seriousness.

Medical and scientific judgment should be exercised in deciding if an event is serious if it does not meet the above definitions, such as an important medical event(s) that may not be immediately life-threatening or result in death or hospitalization but that may jeopardize the subject or may require intervention to prevent one of the above outcomes. Specific examples of such events are intensive treatment in an emergency room or at home for allergic bronchospasm, blood dyscrasias, or convulsions that do not result in hospitalization.

A distinction should be drawn between seriousness and severity of an AE. An AE that is assessed as severe, for example, should not be confused with an SAE. Severity is a category utilized for rating the intensity of the event (see below); both AEs and SAEs will be assessed

for severity grading. An event is defined as “serious” when it meets one of the predefined outcomes as described above.

6.1.2. Assessment of Adverse Events

Each event recorded on the AE CRF will be assessed by the Investigator with regard to the following categories.

6.1.2.1. Severity

Severity of AEs will be graded as one of:

- **Mild:** Awareness of signs or symptoms but easily tolerated. A type of AE that is usually transient and may require only minimal treatment or therapeutic intervention. The event does not generally interfere with usual activities of daily living.
- **Moderate:** A type of AE that is usually alleviated with additional specific therapeutic intervention. The event interferes with usual activities of daily living, causing discomfort but poses no significant or permanent risk of harm to the research subject.
- **Severe:** Incapacitating the ability to do work or to do activities. A type of AE that interrupts usual activities of daily living, or significantly affects clinical status, or may require intensive therapeutic intervention.

6.1.2.2. Relationship to Study Medication

The Investigator or designee, using clinical judgment, will assess the causality/relationship between each AE and the most recently administered study medication (i.e., whether there is a reasonable possibility that the drug caused the event) and record that assessment in the CRF.

Unrelated: The AE is clearly not related to the study medication. The AE is clearly explained by another cause, or exposure to the study medication has not occurred.

Related: The AE may be related to the study medication. The AE and administration of the study medication are considered reasonably related in time, but the AE is more likely explained by the study medication than another cause.

AE reporting will extend from randomization until completion of the End-of-Study Visit. AEs occurring after the end of the clinical trial must be reported if the Investigator considers there is a causal relationship with the study medication.

All AEs, regardless of the relationship to study medication, will be recorded in the CRF.

All reports should contain a brief description of the event, date of onset, date of resolution, severity, treatment required, relationship to study medication, outcome, and whether the event is classified as serious. Whenever possible, the Investigator should group signs or symptoms that constitute a single diagnosis into a single event term. For example, “cough, rhinitis, and sneezing” might be grouped together as “upper respiratory tract infection.”

A treatment-emergent clinically significant abnormal laboratory value should be recorded as an AE.

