3.3. Criteria for Suspension/Termination of Trial

Administration of CST-2032 and CST-107 will be stopped if either of the following occurs:

- Two serious adverse events (SAEs) within the same system organ class (SOC) considered to be related to study drug; or
- Three severe or clinically significant adverse events (AEs) considered to be related to study drug.

The Sponsor reserves the right to terminate this clinical trial at any time. If the clinical trial is terminated prior to scheduled completion, the Investigator will be notified and given any necessary instructions concerning final examinations that are required. If the Investigator, the Sponsor, or the Sponsor's Medical Monitor becomes aware of conditions or events that suggest a possible hazard to subjects if the clinical trial continues, the clinical trial may be terminated after appropriate consultation with the relevant parties.

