11 SAFETY

11.1 Adverse Events

Adverse events (AEs) will be recorded from the time of randomization through end of study. AEs will also be assessed for severity, relationship to study drug, and seriousness. AEs will be considered treatment-emergent if their onset occurs following the date and time of first dose of CST-2032 or matching placebo up to the study completion date. Each TEAE will also be categorized according to the treatment period in which it occurs, in order to attribute and summarize an AE based on treatment received at time of event (i.e., during placebo or active treatment). Events that occur during the washout period between Treatment Period 1 and 2 will be attributed to the treatment received in Period 1, and events occurring after Treatment Period 2 up to the End of Study visit will be attributed to the treatment received in Period 2.

Any missing severity assessments will be assumed to be severe, missing relationship assessments will be assumed to be related, and missing seriousness assessments will be assumed as serious.

An overview of AEs will be produced, including counts and percentages of subjects with any incidences of: treatment-emergent AEs (TEAEs), serious AEs (SAEs), related AEs, unrelated AEs, AEs by maximum severity, AEs leading to treatment withdrawal and AEs leading to death.

Adverse events will be coded based on the Medical Dictionary for Regulatory Affairs (MedDRA 24.1) for reporting by system organ class (SOC) and preferred term (PT) in descending order of overall incidence.

Summaries of adverse events by SOC and PT will include the following types:

- TEAEs;
- SAEs; and
- Related AEs.

A summary of TEAEs by SOC, PT, and maximum severity will also be prepared.

A comprehensive listing of all AEs will be provided in a by-subject data listing. In addition, the following listings will be provided:

- SAEs;
- Related AEs; and
- AEs leading to study drug termination

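### The definitions of Related and Unrelated in Protocol 6.1.2.2 contradict each other and the section's own causality question, so an event where the drug is plausible but not the likelier cause can be classified either way

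*Protocol*

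**What the plan says.** Protocol 6.1.2.2 opens with one question for every adverse event: "whether there is a reasonable possibility that the drug caused the event". It then offers two categories.

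- **Unrelated** begins "The AE is clearly not related to the study medication". It goes on to require that a different explanation be clear or that the subject took no drug.
- **Related** begins by saying only that the drug may be involved. A further sentence asks for a plausible time relation and ends "but the AE is more likely explained by the study medication than another cause".

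SAP 11.1 keeps the same two categories; its overview lists "related AEs, unrelated AEs, AEs by maximum severity". It also says that "missing relationship assessments will be assumed to be related", which deals with blank fields and not with doubtful judgements.

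The label is used in several places:

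- **Summaries:** Protocol 8.7.1 and SAP 11.1 tabulate related events by system organ class and preferred term.
- **Subject-level rule:** Protocol 3.2 ends a subject's dosing after one serious event that the investigator deems related.
- **Trial-level rule:** Protocol 3.3 stops administration on either of two counts. One is "Two serious adverse events (SAEs) within the same system organ class (SOC) considered to be related to study drug"; the other is three related events that are severe or clinically significant.
- **Reporting:** Protocol 6.1.3 attributes related events to CST-2032 for expedited reporting unless the investigator is confident that CST-107 was the cause. Under 6.1.2.2 and 6.1.4, events arising after the trial are reported only if judged drug-related.

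**The concern.** A two-category causality scale works only if every event fits exactly one category. Here one category needs the drug to be the likelier explanation and the other needs it to be clearly excluded. Events between those two points have no home, although the opening question would count them as drug-related.

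Such events are plausible in this trial. Protocol 1.1.1 lists tremor, palpitations, headache and dizziness among the commonest adverse events of CST-2032 given alone, and Protocol 4.4 lists rest tremor among the diagnostic features of Parkinson's disease. An investigator who sees worsened tremor may think the disease the likelier cause and still think the drug possible. This is an illustration, not a forecast: Protocol 1.1.1 also reports no tremor, palpitations or dizziness in the phase 1 study at the dose combination planned here.

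At stake is whether a related event means the same thing across up to 20 sites, and whether the rules in Protocol 3.2 and 3.3 act on a consistent count.

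**Working it through.** No figure in the plan bears on this and no arithmetic applies. The check sets the three thresholds side by side, tests each possible state of an event against them, and looks for a rule that settles the remainder.

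**Thresholds, all from Protocol 6.1.2.2**

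| Element | Strength of drug causation required |
|---|---|
| Opening question | Reasonable possibility |
| Related, first sentence | May be related |
| Related, last clause | Drug likelier than another cause |
| Unrelated, first sentence | Drug clearly excluded |
| Unrelated, second sentence | Another cause is clear, or no exposure |

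**Possible states of an event**

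| State | Related, in full? | Unrelated, in full? | Opening question |
|---|---|---|---|
| (a) Exposed, related in time, drug the likelier cause | Yes | No | Yes |
| (b) Exposed, another cause clear, drug clearly excluded | No | Yes | No |
| (c) Exposed, drug reasonably possible, another cause as likely or likelier but not clear | No, fails the last clause | No, fails both tests of clarity | Yes |
| (d) Not exposed | No | Yes | No |

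State (c) is the gap. It meets the opening question and the first sentence of Related, and it fails the last clause of Related and both sentences of Unrelated.

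**Search for a rule covering (c).** Neither document contains an intermediate category or a tie-break. The default to related in SAP 11.1 applies only when the assessment is missing; an investigator who enters a judgement in state (c) has not left it missing.

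**What follows.** An investigator guided by the first sentence of Related records (c) as related. One guided by its last clause excludes it from Related and has only Unrelated left. Each can cite the protocol.

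**Reach.** The triggers in Protocol 3.2 and 3.3 are one, two and three related events. With counts that small, the label on a single event can decide whether a trigger is met.

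**The case against.** **Related opens with a low bar, so (c) fits there.** The first sentence of Related, read alone, does cover state (c) and agrees with the opening question. But the definition continues, and its last clause withdraws what the first sentence grants. The accurate description is a definition that contradicts itself; (c) is homeless only when each definition is read in full.

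**A reader might infer that the related-event rate is biased downward.** The documents do not support this. State (c) fails Unrelated as well, and an investigator forced to choose may follow the first sentence of Related. Nor do the documents show how often such events will have a competing cause, or that sites will in fact differ.

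**A reader might infer that every event with a reasonable possibility of drug cause falls in the gap.** It does not. State (a) fits Related; only (c) is affected.

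**The main safety evidence does not depend on causality.** This stands. The primary endpoint in Protocol 2.2 names adverse event and serious event rates without a causality filter. All events are recorded, and all serious events up to the final visit are reported within 24 hours, whatever the relationship. Treatment-emergent events are assigned to a treatment by start date. Assessment is blinded, so nothing suggests that misclassification would favour one treatment. Ongoing blinded safety review, the DSMB and the discretion given to the Medical Monitor and investigator also operate without the label. None of this helps the items that use the label directly.

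**A reasonable-possibility test is also a judgement.** True. Changing the definitions removes the contradiction, not all variation between assessors.

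**Conclusion.** The point holds as an internal inconsistency in Protocol 6.1.2.2. For an exposed subject, an event where the drug is reasonably possible but not the likelier cause meets neither full definition, and the protocol permits either label.

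The affected items are the related-event summaries, the related-event triggers in Protocol 3.2 and 3.3, the attribution for expedited reporting in 6.1.3, and the reporting of events after the trial. Comparisons of all treatment-emergent events and of all serious events between treatments are untouched.

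Neither size nor direction can be determined: the documents give no event rates by causality category and no indication of which sentence investigators will follow. The conclusion assumes that the two definitions are applied in full and that no separate completion guide, outside these documents, settles the intermediate case. It should be corrected, because a stated rule classifies inconsistently and the correction is small; it does not undermine the primary safety analysis.

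**What to change.** Make the two categories exhaustive and tie both to the question that opens Protocol 6.1.2.2:

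- **Related:** a reasonable possibility exists that the study medication played a causal role.
- **Unrelated:** no such possibility exists.

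Remove the comparative clause from Related and the requirement of clarity from Unrelated, and carry the same text into the CRF guidance. SAP 11.1 can keep its two categories and its default for missing assessments.

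Because Protocol 3.2, 3.3 and 6.1.3 all use the label, the sponsor should reconcile those sections with the single definition and confirm what each is meant to count. What those rules should require is for the sponsor to decide.

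**Cost.** Two sentences in the protocol, matching CRF guidance, and an amendment. More events may be classed as related. The SAP is tied to protocol Amendment 10 and CRF version 7.0. If events have already been assessed under the current wording, they may need re-review, or the study report should state that two definitions were in use and from when.
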